11. History of intolerance to 5-MeO-DMT, dimethyltryptamine (DMT), or related compounds
12. Any nasal obstruction, blockage, or symptoms of congestion
13. Any personal or family history of malignant hyperthermia

14. Disposition judged by the Investigator (or delegate) to be incompatible with establishment of rapport with study team and/or safe exposure to BPL-003
15. Presence of acute or chronic illness or infection or history of chronic illness or infection sufficient to invalidate the patient's participation in the study or make it unnecessarily hazardous
16. Presence or history of severe adverse reaction to any drug or drug excipient
17. Female patients who are pregnant or lactating or are of childbearing potential and not willing to use adequate forms of contraception during the study and for 1 month after completion of the study as described in the protocol
18. Male patients who are sexually active and not willing to use adequate forms of contraception during the study or for 1 month after completion of the study as described in the protocol
19. Patients who have taken part in a clinical research study in the last 4 weeks, whether or not they received an investigational medicinal product as part of that research study
20. Current criminal justice involvement with legal proceedings, which in the opinion of the Investigator means the participant may fail to complete the study protocol due to inability to complete study visits with the study site team
21. Unable to communicate in English to a level required to accept standard care and psychological intervention
22. Patients who, in the opinion of the Investigator, are not suitable to participate in the study for any other reason not mentioned in the entry criteria

Psychiatric Exclusion Criteria:

23. Personal or first-degree family history of schizophrenia, bipolar disorder, psychotic disorder (unless substance induced or due to a medical condition), delusional disorder, paranoid disorder or schizoaffective disorder, as defined by DSM-5. Personal history determined by medical records and positive diagnoses on the Mini-International Neuropsychiatric Interview (MINI) to be confirmed by the Investigator
24. Any major psychiatric disorders, with the exception of mild or moderate anxiety and/or depression, as determined by a MINI and confirmed by the Investigator
25. A clinical diagnosis of post-traumatic stress disorder (as determined by MINI)

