9.8. Montgomery–Asberg Depression Rating Scale

The Montgomery–Åsberg Depression Rating Scale (MADRS) will be completed at the visits outlined in [Table 1](#).

Via the electronic Clinical Outcome Assessment (eCOA), an appropriately trained member of the study team will use the Structured Interview Guide for the MADRS (SIGMA) to interview the subject moving from broad questions about symptoms to more detailed ones which allow the precise rating of symptom severity. The MADRS is a 10-item diagnostic questionnaire used to measure the severity of depressive episodes in patients with mood disorders (Williams, 2008). A higher MADRS score indicates more severe depression, and each item yields a score of 0 to 6. The overall score ranges from 0 to 60. The questionnaire includes questions on the following symptoms: (1) apparent sadness, (2) reported sadness, (3) inner tension, (4) reduced sleep, (5) reduced appetite, (6) concentration difficulties, (7) lassitude, (8) inability to feel, (9) pessimistic thoughts, and (10) suicidal thoughts. The usual cutoff points are:

- 0 to 6 = normal/symptom absent
- 7 to 19 = mild depression
- 20 to 34 = moderate depression
- >34 = severe depression.

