9.12. Patient Global Impression of Change

A brief PGIC will be completed at the visits outlined in [Table 1](#). The PGIC uses a 7-item scale to rate total improvement reported by patient whether or not it is due to drug treatment. The patient will report their own current condition compared to that at Screening on the following scale:

- 0 = Not assessed
- 1 = Very much improved
- 2 = Much improved
- 3 = Minimally improved
- 4 = No change
- 5 = Minimally worse
- 6 = Much worse
- 7 = Very much worse

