19 ATTACHMENTS

19.1 Table of contents for data display specifications

For overall page layout refer to Appendix B: Sample page .

The numbering in the tables below will take precedence over the numbering in the shells.

The following tables and figures will be produced (templates provided in Section 19.2.1 and 19.2.2):

Table	Description	Population	Source Listing	Template (Shells below)
10.1	Summary of patient disposition	Safety	16.2.1.2, 16.2.1.3, 16.2.3.1	T_SD1
14.1	DEMOGRAPHIC DATA			
14.1.1	Summary of demographic characteristics	Safety	16.2.4.1	T_DM1
14.1.2	Summary of alcohol and drug abuse use data	Safety	16.2.4.4, 16.2.4.5	T_AUDU
14.2	PHARMACOKINETIC AND PHARMACODYNAMIC DATA			
14.2.1.1	Summary of 5MeO-DMT plasma pharmacokinetic concentration-time data [units]	PK Concentration	16.2.6.1	T_PK1
14.2.1.2	Summary of bufotenine plasma pharmacokinetic concentration-time data [units]	PK Concentration	16.2.6.1	T_PK1
14.2.1.3	Summary of 5-methoxyindolacetic acid plasma pharmacokinetic concentration-time data by treatment group [units]	PK Concentration	16.2.6.1	T_PK1
14.2.1.4	Summary of 5-MeO-DMT-N-Oxide plasma pharmacokinetic concentration-time data by treatment group [units]	PK Concentration	16.2.6.1	T_PK1
14.2.2	Summary of Stanford Expectation of Treatment Scale (SETS)	ITT	16.2.6.2	T_PD1
14.2.3.1	Summary of Mystical Experience Questionnaire (MEQ-30) [intent-to-treat population]	ITT	16.2.6.3	T_PD1
14.2.3.2	Summary of Mystical Experience Questionnaire (MEQ-30) [per protocol population]	PP	16.2.6.3	T_PD1
14.2.3.3	Summary of complete mystical experience [intent-to-treat population]	ITT	16.2.6.3	T_PD3
14.2.3.4	Summary of complete mystical experience [per protocol population]	PP	16.2.6.3	T_PD3
14.2.4	Summary of Ego Dissolution Inventory (EDI)	ITT	16.2.6.4	T_PD1
14.2.5	Summary of 5-Level EuroQol 5-Dimension (EQ-5D-5L)	ITT	16.2.6.5	T_PD4
14.2.6.1	Summary of Timeline Follow-Back (TLFB)) [intent-to-treat population]	ITT	16.2.6.6	T_PD1a
14.2.6.2	Summary of Timeline Follow-Back (TLFB) [per protocol population]	PP	16.2.6.6	T_PD1a
14.2.7.1	Summary of Montgomery-Åsberg Depression Rating Scale (MADRS)	ITT	16.2.6.7	T_PD2

Table	Description	Population	Source Listing	Template (Shells below)
14.2.7.2	Summary of patients with 50% reduction from baseline of MADRS scores	ITT	16.2.6.7	T_PD2a
14.2.7.3	Summary of patients in remission based on MADRS scores ≤ 10	ITT	16.2.6.7	T_PD2b
14.2.8	Summary of Alcohol Craving Questionnaire (ACQ)	ITT	16.2.6.8	T_PD2

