									n	Mean	SD	Median	Min	Max
Apparent Sadness	Treatment 1 (N=xx)													
↓														
Total MADRS Score	Treatment 1 (N=xx)													

Source: Listing 16.2.xx

Programming notes: For MADRS, include all individual questions treated as continuous data
Continued for all scores (subscales and/or total score) & time points for all questionnaires described in Appendix A. Update column 1 to match the data
For Alcohol Craving questionnaire, the first column will be "Scoring Item"

Template T_PD2a

Table 14.3.4.xx Summary of patients with 50% reduction from baseline of MADRS scores

Treatment	Responder at Day 28 n (%)	Responder at Day 56 n (%)	Responder at Day 84 n (%)
Treatment 1 (N=xx)			

Source: Listing 16.2.xx

Note: Percentages are based on the number of non-missing observations

Programming notes: Continued with all time points

Template T_PD2b

Table 14.3.4.xx Summary of patients in remission based on MADRS scores ≤ 10

Treatment	Planned Relative Time	Total MADRS score ≤ 10 n (%)
Treatment 1 (N=xx)	Time 1	

Source: Listing 16.2.xx

Note: Percentages are based on the number of non-missing observations

Programming notes: Continued with time points.

Template T_PD3

Table 14.2.2.xx Summary of complete mystical experience

Treatment 1 (N=xx)	
Planned Relative Time	n (%)
Time 1	

Source: Listing 16.2.xx

A complete mystical experience is defined as a patient scoring 3 or more on each of the four subdomains

Programming notes: Continued for all timepoints

Template T_PD4

Table 14.2.2.xx Summary of 5-Level EuroQoL 5-Dimension (EQ-5D-5L)

Item Assessed	Question	Planned Relative Time	Treatment 1 (N=xx)
Mobility (%)	I have no problems in walking about	Time 1	
		Time 2	
	I have slight problems in walking about	Time 1	
		Time 2	
	I have moderate problems in walking about	Time 1	
Self-care (%)	↓		
	I have no problems washing or dressing myself	Time 1	
	↓	Time 2	
Usual activities (%)	I have no problems doing my usual activities	Time 1	
	↓		
Pain/Discomfort (%)	I have no pain or discomfort	Time 1	
	↓		
Anxiety/Depression (%)	I am not anxious or depressed	Time 1	
	↓		
How good or bad your health is today (mm)	n	Time 1	
	Mean		
	SD		
	Median		
	Min		
	Max		

Programming notes: Continued with all Items assessed, questions, treatment groups and time points.

Template T_PD5

Table 14.2.2.xx Summary of Montgomery-Asberg Depression Rating Scale (MADRS)

Question	Treatment	Planned								Change from Baseline					

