		Relative Time	n	Mean	SD	Median	Min	Max		n	Mean	SD	Median	Min	Max
Apparent Sadness	Treatment 1 (N=xx)														
↓															
Total MADRS Score	Treatment 1 (N=xx)														

Source: Listing 16.2.xx

Programming notes: Continued with all questions, and time points.

Template T_PD6

Table 14.2.3.xx Summary of Clinical Global Impression-Severity (CGI-S)

Treatment	Planned								Change from Baseline					
	Relative Time	n	Mean	SD	Median	Min	Max		n	Mean	SD	Median	Min	Max
Treatment 1 (N=xx)														

Source: Listing 16.2.xx

Programming notes: Continued for all time points. Treat the data as continuous
Change from baseline is not required for PGIC

Template T_AE1

Table 14.3.3.xx Summary of treatment-emergent adverse events

System Organ Class*	Preferred Term	Treatment 1 (N=xx)
		n (%)
Number of patients with TEAEs		x (xx.x)
Gastrointestinal disorders	Total number of patients	x (xx.x)
	Abdominal discomfort	x (xx.x) [xx]
	Abdominal pain	x (xx.x) [xx]
	↓	
Nervous system disorders	Total number of patients	x (xx.x)
	Dizziness	x (xx.x) [xx]
	Headache	x (xx.x) [xx]
	↓	
↓	↓	

Source: Listing 16.2.xx

n = number of patients (patients with >1 TEAE are counted only once per system organ class and preferred term)

[] = number of TEAEs

*Coded using MedDRA version xx.x

rogramming notes: SOC and PTs are sorted in decreasing order of frequency
Presented for all applicable MedDRA system organ classes and terms.

Template T_AE2

Table 14.3.3.xx Overall summary of treatment-emergent adverse events

Number of Patients with	Treatment 1 (N=xx)	
	n (%)	
Any TEAE	x (xx.x)	[xx]
Any serious TEAE	x (xx.x)	[xx]
Any drug-related TEAE	x (xx.x)	[xx]
Any TEAE leading to withdrawal	x (xx.x)	[xx]
Any TEAE with mild as worst severity	x (xx.x)	
Any TEAE with moderate as worst severity	x (xx.x)	
Any TEAE with severe as worst severity	x (xx.x)	
Any TEAE with life-threatening as worst severity	x (xx.x)	

Source: Listing 16.2.xx

n = number of patients

[] = number of TEAEs

Template T_AE3

Table 14.3.3.xx Summary of treatment-emergent adverse events by maximum severity

System Organ Class*	Preferred Term	Severity	Treatment 1 (N=xx) n (%)
Number of TEAEs		Mild	x (xx.x)
		Moderate	x (xx.x)
		↓	
Gastrointestinal disorders	Total number of patients	Mild	x (xx.x)
		Moderate	x (xx.x)
	Abdominal discomfort	Mild	x (xx.x)
	Abdominal pain	Mild	x (xx.x)
		↓	

Source: Listing 16.2.xx

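### The MADRS remission table counts patients who were already at or below 10 before dosing, and the response table has no baseline floor

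*SAP*

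**What the plan says.** SAP 19.1 lists two MADRS threshold tables on the ITT population. Table 14.2.7.2 is "Summary of patients with 50% reduction from baseline of MADRS scores" (template T_PD2a, Days 28, 56 and 84). Table 14.2.7.3 is "Summary of patients in remission based on MADRS scores ≤ 10" (template T_PD2b). Both shells in SAP 19.2.1 carry the footnote that "Percentages are based on the number of non-missing observations". SAP section 9 defines ITT as dosed patients with a PD measure. SAP Appendix A 1.2 describes only the total score and says nothing about response, remission or a minimum baseline.

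Protocol 5.2.1 requires moderate to severe alcohol use disorder and sets no MADRS threshold. The psychiatric exclusions rule out "Any major psychiatric disorders, with the exception of mild or moderate anxiety and/or depression", so mild or moderate depression is allowed but not needed. Protocol 9.8 gives the bands, starting with "0 to 6 = normal/symptom absent", then mild from 7 to 19 and moderate from 20 to 34.

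The MADRS endpoint in Protocol 3.3 and SAP 4.2.3 is change from baseline at Days 28, 56 and 84. Response and remission are not listed endpoints.

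On a smaller matter, T_PD6 (CGI-S and PGIC) instructs: "Continued for all time points. Treat the data as continuous". Protocol 9.11 and 9.12 include a code 0 on both scales, worded for PGIC as "0 = Not assessed", while 1 is the best clinical state.

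**The concern.** Remission presumes that the patient had the condition at the start. Here the normal band, 0 to 6, lies wholly inside the remission band, and nothing ensures that a patient began above it. The figure therefore depends on who was enrolled as well as on what happened after dosing. The trial is open-label with no control group, so no comparator arm would show how much of the rate was present beforehand.

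The label also invites a false comparison. Protocol 1.4.2.4 reports remission by the same cut-off in another 5-MeO-DMT study, where 7 of 8 patients with treatment-resistant depression met it. Those patients were enrolled for depression; the patients in this trial are not.

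For response, a proportional criterion without a floor lets very small movements count at low baselines and fails at zero.

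**Working it through.** The plan states no figure for these outputs, so there is nothing to reproduce. The check applies the display rules to n = 12, the planned maximum (Protocol 11.2). The documents give no baseline MADRS distribution, so every split below is an assumption.

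**Remission (T_PD2b), no change in anyone.** Let k be the number with baseline MADRS of 10 or less.
- Rule as written: rate = k/12.
- Restricted to baseline above 10: rate = 0/(12 − k).

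| k | As written | Restricted |
|---|---|---|
| 0 | 0/12 = 0% | 0/12 = 0% |
| 3 | 3/12 = 25% | 0/9 = 0% |
| 6 | 6/12 = 50% | 0/6 = 0% |
| 9 | 9/12 = 75% | 0/3 = 0% |
| 12 | 12/12 = 100% | not estimable |

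With no effect, the reported rate is the baseline share at or below 10, whatever that share is.

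**Response (T_PD2a).** The smallest whole-point fall that halves a baseline b is b/2 rounded up:
- b = 1 or 2: 1 point
- b = 3 or 4: 2 points
- b = 5 or 6: 3 points
- b = 9 or 10: 5 points
- b = 20: 10 points
- b = 34: 17 points

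At b = 0 the percentage change has a zero denominator. A programmer who tests whether the visit score is at most half of baseline would count 0 to 0 as a response (0 ≤ 0). One who computes a percentage would get no value. The SAP does not choose.

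The direction is not fixed. Suppose 6 patients start above 10 and 3 of them halve their score, which is 3/6 = 50%. Add 6 low-baseline patients:
- none halve: (3 + 0)/12 = 25%
- all halve: (3 + 6)/12 = 75%

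**Code 0 (T_PD6).** If m of 12 patients carry a 0 that is averaged and the rest score s, the mean is (12 − m)s/12. For m = 1:
- s = 3: 33/12 = 2.75, a shift of −0.25
- s = 4: 44/12 = 3.67, a shift of −0.33
- s = 5: 55/12 = 4.58, a shift of −0.42

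A post-dose 0 moves the mean toward better. A 0 at the CGI-S baseline works the other way. One patient truly at 4 throughout would show a change of +4 instead of 0, moving the mean change by +4/12 = +0.33, toward worse.

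**The case against.** The best defence is that little rests on these tables. MADRS is an exploratory measure, no hypothesis is tested, and no primary or secondary endpoint is touched. Table 14.2.7.1 gives scores and change from baseline for everyone, and Listing 16.2.6.7 gives patient-level totals for at most 12 people, so a careful reader could see who started low. T_PD2b runs over time points without excluding baseline, so it may even show the pre-dose count. All of this stands and limits the severity. It does not correct a rate labelled as remission.

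A second objection is that a floor of 10 is not in the documents and leaves an edge: a fall from 11 to 10 would count as remission. That also stands, and it is why retitling the table is offered as an alternative.

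A reader might infer more than the documents support:
- **That never-depressed patients are being counted.** The documents show only that depression at baseline is not required. They say nothing about lifetime history or about how many patients start low.
- **That low-baseline patients automatically become responders.** Their score must still halve, and those whose score does not halve dilute the rate.
- **That the SAP orders code 0 to be averaged.** It is silent. A code meaning not assessed reads naturally as missing, and SAP 12.1 rules out imputation. Harm needs a 0 to be recorded and then left in. The 0 in the CGI-S listing shell is a dummy entry; the exposure shell likewise shows a 25 mg oral tablet for a nasal powder.
- **That every error favours the drug.** Response bias can go either way, and a baseline 0 on CGI-S would work against the drug.

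**Conclusion.** The remission point holds under the rule as written. Table 14.2.7.3 would report as in remission any patient who was at or below 10 before dosing and stayed there. With no treatment effect the rate equals the baseline share at or below 10, for example 25%, 50% or 75% for 3, 6 or 9 of 12 patients. The identity does not depend on the assumed split; the percentages do.

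The response point holds as a gap in definition. There is no floor, no rule at baseline 0, and no statement that a reduction greater than 50% also qualifies, and the direction of bias is unknown. The code 0 point is a request for clarification only.

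The affected outputs are exploratory and descriptive. The change is worth making because it is cheap and because an uncontrolled study offers no other check on a remission rate.

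**What to change.** 1. **T_PD2a and T_PD2b:** restrict both to patients with baseline MADRS above 10 and print that number as the denominator. Alternatively, retitle T_PD2b as the number of patients with MADRS at or below 10, drop the word remission, and show the baseline count beside each visit.
2. **T_PD2a:** define response as a reduction of at least 50% from baseline. The floor removes the baseline 0 problem; if no floor is adopted, state how baseline 0 is handled.
3. **Appendix A 1.2:** record both definitions there. Keep mean change from baseline for all patients in Table 14.2.7.1.
4. **T_PD6 (minor):** state that code 0 on CGI-S and PGIC is set to missing before means are computed, and report how many there were.

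The cost is a few SAP definitions and programming notes, with no new data. The drawback is small denominators: with 9 of 12 patients at or below 10 at baseline, only 3 would remain, and with all 12 there would be no rate to report. Retitling avoids that.

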19.2 Data display specifications

19.2.1 Table Outlines

Template T_SD1

Table 10.1 Summary of patient disposition

Population	Status	Reason for Discontinuation/Withdrawal	All Patients (N=xx) n (%)
Screened	Total		
	Included		
	Excluded	Not satisfying inclusion/exclusion criteria Declined to participate Other	
Safety	Included		xx
	Completed		xx (xx)
	Withdrawn		xx (xx)
		Death	xx (xx)
		Adverse Events	xx (xx)
		Withdrawal by patient	xx (xx)
		Study terminated by Sponsor	xx (xx)
		Lost to follow-up	xx (xx)
		Other	xx (xx)
PK concentration	Included		xx (xx)
Intent-to-treat	Included		xx (xx)
Per protocol			

Source: Listing 16.2.xx

Template T_DM1

Table 14.1 Summary of demographic characteristics

Variable	Statistics	Treatment 1 (N=xx)
Age (y)	n	
	Mean	
	SD	
	Median	
	Min	
	Max	
Sex (%)	Female	
	Male	
Race (%)	American Indian or Alaskan Native	
	Asian	
	Black	
	Native Hawaiian or other Pacific Islander	
	White	
	Other	
Ethnicity (%)	Hispanic or Latino	
	Not Hispanic or Latino	
Height (cm)	n	
	Mean	
	SD	
	Median	
	Min	
	Max	
Weight (kg)	n	
	Mean	
	SD	
	Median	
	Min	
	Max	

Source: Listing 16.2.xx

Programming notes: Continued with all additional demographic characteristics

Template T_AUDU

Table 14.2.2.xx Summary of alcohol and drug abuse use history data

Variable	Statistics	Treatment 1 (N=xx)
Age Drinking Problem	n	
Recognised (years)	Mean	
	SD	
	Median	
	Min	
	Max	
AUD DSM-V Score	n	
	Mean	
	SD	
	Median	
	Min	
	Max	
AUD Severity (number of	Mild (2-3 criteria)	
DSM-V Symptoms) (%)	Moderate (4-5 criteria)	
	Severe (6 or more	
	criteria)	
Drug 1 (%)	Yes	
	No	
Drug 2 (%)	Yes	
	No	

Source: Listing 16.2.xx

AUD= Alcohol use disorder

Programming notes: Continued with all Items assessed, and drug used as recorded

Template T_PK1

Table 14..2.xx Summary of 5-MeO-DMT plasma pharmacokinetic concentration-time data [units]

Treatment	{Add. time var.}	Planned Relative Time	n	No. Imputed	Mean	95% CI (Lower,Upper)	SD	%CVb	Median	Min	Max
Treatment 1 (N=xx)		5 min	x	x	xxxx.x	(xxxx.x,xxxx.x)		xx.x	xxxx.x	xxxx	xxxx
		15 min	x	x	xxxx.x	(xxxx.x,xxxx.x)	xx.xx	xx.x	xxxx.x	xxxx	xxxx
		60 min	x	x	xxxx.x	(xxxx.x,xxxx.x)	xx.xx	xx.x	xxxx.x	xxxx	xxxx

Source: Listing 16.2.xx

Programming notes: Continued with all timepoints

Template T_PD1

Table 14.2.2.xx Summary of Stanford Expectations of Treatment Scale (SETS)

Score	Treatment	Planned Relative Time	n	Mean	SD	Median	Min	Max
Positive Expectancy	Treatment 1 (N=xx)							
Negative Expectancy	Treatment 1 (N=xx)							

Source: Listing 16.2.xx

Programming notes: For EDI and visual analogue scale, the first column will be "Score (mm)". Include all subscales as stated in appendix A

Template T_PD1a

Table 14.2.2.xx Summary of Timeline Follow-Back (TLFB) [intent-to-treat population]

Scoring Item	Treatment	Planned Relative Time	n	Mean	SD	Median	Min	Max	Change from Baseline					
									n	Mean	SD	Median	Min	Max
Longest continuous number of abstinence (days)	Treatment 1 (N=xx)		x	x.x	x.xx	x.x	x	x						
Max number of standard units of alcohol consumed on any one day	Treatment 1 (N=xx)	85 Days Prior Day-3	x	x.x	x.xx	x.x	x	x						
		Day 14	x	x.x	x.xx	x.x	x	x						
		Day 28	x	x.x	x.xx	x.x	x	x						
		Day 56	x	x.x	x.xx	x.x	x	x						
		Day 84	x	x.x	x.xx	x.x	x	x						
Number of Heavy Drinking Days (HDD)	Treatment 1 (N=xx)	85 Days Prior Day-3	x	x.x	x.xx	x.x	x	x						
		Day 14	x	x.x	x.xx	x.x	x	x						
		Day 28	x	x.x	x.xx	x.x	x	x						
		Day 56	x	x.x	x.xx	x.x	x	x						
		Day 84	x	x.x	x.xx	x.x	x	x						
Number of days after dosing to first drink	Treatment 1 (N=xx)		x	x.x	x.xx	x.x	x	x						
Number of days after dosing to first HDD	Treatment 1 (N=xx)		x	x.x	x.xx	x.x	x	x						
Average number of standard units of alcohol consumed per week	Treatment 1 (N=xx)	85 Days Prior Day-3	x	x.x	x.xx	x.x	x	x						
		Day 14	x	x.x	x.xx	x.x	x	x	x	x.x	x.xx	x.x	x	x
		Day 28	x	x.x	x.xx	x.x	x	x	x	x.x	x.xx	x.x	x	x
		Day 56	x	x.x	x.xx	x.x	x	x	x	x.x	x.xx	x.x	x	x
		Day 84	x	x.x	x.xx	x.x	x	x	x	x.x	x.xx	x.x	x	x
Percentage of Heavy Drinking Days (PHDD)	Treatment 1 (N=xx)	85 Days Prior Day-3	x	x.x	x.xx	x.x	x	x						
		Day 14	x	x.x	x.xx	x.x	x	x	x	x.x	x.xx	x.x	x	x
		Day 28	x	x.x	x.xx	x.x	x	x	x	x.x	x.xx	x.x	x	x
		Day 56	x	x.x	x.xx	x.x	x	x	x	x.x	x.xx	x.x	x	x
		Day 84	x	x.x	x.xx	x.x	x	x	x	x.x	x.xx	x.x	x	x
Percentage of Drinking Days (PDD)	Treatment 1 (N=xx)		x	x.x	x.xx	x.x	x	x	x	x.x	x.xx	x.x	x	x
Mean Units per Day (UPD)	Treatment 1 (N=xx)		x	x.x	x.xx	x.x	x	x	x	x.x	x.xx	x.x	x	x

Abstinence: Percentage of Treatment 1 (N=xx) x x.x x.xx x.x x x x x.x x.xx x.x x x

Abstinent Days (PAD)

Source: Listing 16.2.xx

Note: 85 Days Prior Day -3 = 85 Days Prior Day -3 (or start of detox)

Programming notes: Continued with all the timepoints (85 Days Prior Day-3, Day 14, Day 28, Day 56 and Day 84) for PDD, UPD and PAD

Template T_PD2

Table 14.2.2.xx Summary of Montgomery-Åsberg Depression Rating Scale (MADRS) [intent-to-treat population]

Question	Treatment	Planned Relative Time	n	Mean	SD	Median	Min	Max	Change from Baseline					
									n	Mean	SD	Median	Min	Max
Apparent Sadness	Treatment 1 (N=xx)													
↓														
Total MADRS Score	Treatment 1 (N=xx)													

Source: Listing 16.2.xx

Programming notes: For MADRS, include all individual questions treated as continuous data
Continued for all scores (subscales and/or total score) & time points for all questionnaires described in Appendix A. Update column 1 to match the data
For Alcohol Craving questionnaire, the first column will be "Scoring Item"

Template T_PD2a

Table 14.3.4.xx Summary of patients with 50% reduction from baseline of MADRS scores

Treatment	Responder at Day 28 n (%)	Responder at Day 56 n (%)	Responder at Day 84 n (%)
Treatment 1 (N=xx)			

Source: Listing 16.2.xx

Note: Percentages are based on the number of non-missing observations

Programming notes: Continued with all time points

Template T_PD2b

Table 14.3.4.xx Summary of patients in remission based on MADRS scores ≤ 10

Treatment	Planned Relative Time	Total MADRS score ≤ 10 n (%)
Treatment 1 (N=xx)	Time 1	

Source: Listing 16.2.xx

Note: Percentages are based on the number of non-missing observations

Programming notes: Continued with time points.

Template T_PD3

Table 14.2.2.xx Summary of complete mystical experience

Treatment 1 (N=xx)	
Planned Relative Time	n (%)
Time 1	

Source: Listing 16.2.xx

A complete mystical experience is defined as a patient scoring 3 or more on each of the four subdomains

Programming notes: Continued for all timepoints

Template T_PD4

Table 14.2.2.xx Summary of 5-Level EuroQoL 5-Dimension (EQ-5D-5L)

Item Assessed	Question	Planned Relative Time	Treatment 1 (N=xx)
Mobility (%)	I have no problems in walking about	Time 1	
		Time 2	
	I have slight problems in walking about	Time 1	
		Time 2	
	I have moderate problems in walking about	Time 1	
Self-care (%)	↓		
	I have no problems washing or dressing myself	Time 1	
	↓	Time 2	
Usual activities (%)	I have no problems doing my usual activities	Time 1	
	↓		
Pain/Discomfort (%)	I have no pain or discomfort	Time 1	
	↓		
Anxiety/Depression (%)	I am not anxious or depressed	Time 1	
	↓		
How good or bad your health is today (mm)	n	Time 1	
	Mean		
	SD		
	Median		
	Min		
	Max		

Programming notes: Continued with all Items assessed, questions, treatment groups and time points.

Template T_PD5

Table 14.2.2.xx Summary of Montgomery-Asberg Depression Rating Scale (MADRS)

Question	Treatment	Planned								Change from Baseline					
		Relative Time	n	Mean	SD	Median	Min	Max		n	Mean	SD	Median	Min	Max
Apparent Sadness	Treatment 1 (N=xx)														
↓															
Total MADRS Score	Treatment 1 (N=xx)														

Source: Listing 16.2.xx

Programming notes: Continued with all questions, and time points.

Template T_PD6

Table 14.2.3.xx Summary of Clinical Global Impression-Severity (CGI-S)

Treatment	Planned								Change from Baseline					
	Relative Time	n	Mean	SD	Median	Min	Max		n	Mean	SD	Median	Min	Max
Treatment 1 (N=xx)														

Source: Listing 16.2.xx

Programming notes: Continued for all time points. Treat the data as continuous
Change from baseline is not required for PGIC

Template T_AE1

Table 14.3.3.xx Summary of treatment-emergent adverse events

System Organ Class*	Preferred Term	Treatment 1 (N=xx)
		n (%)
Number of patients with TEAEs		x (xx.x)
Gastrointestinal disorders	Total number of patients	x (xx.x)
	Abdominal discomfort	x (xx.x) [xx]
	Abdominal pain	x (xx.x) [xx]
	↓	
Nervous system disorders	Total number of patients	x (xx.x)
	Dizziness	x (xx.x) [xx]
	Headache	x (xx.x) [xx]
	↓	
↓	↓	

Source: Listing 16.2.xx

n = number of patients (patients with >1 TEAE are counted only once per system organ class and preferred term)

[] = number of TEAEs

*Coded using MedDRA version xx.x

rogramming notes: SOC and PTs are sorted in decreasing order of frequency
Presented for all applicable MedDRA system organ classes and terms.

Template T_AE2

Table 14.3.3.xx Overall summary of treatment-emergent adverse events

Number of Patients with	Treatment 1 (N=xx)	
	n (%)	
Any TEAE	x (xx.x)	[xx]
Any serious TEAE	x (xx.x)	[xx]
Any drug-related TEAE	x (xx.x)	[xx]
Any TEAE leading to withdrawal	x (xx.x)	[xx]
Any TEAE with mild as worst severity	x (xx.x)	
Any TEAE with moderate as worst severity	x (xx.x)	
Any TEAE with severe as worst severity	x (xx.x)	
Any TEAE with life-threatening as worst severity	x (xx.x)	

Source: Listing 16.2.xx

n = number of patients

[] = number of TEAEs

Template T_AE3

Table 14.3.3.xx Summary of treatment-emergent adverse events by maximum severity

System Organ Class*	Preferred Term	Severity	Treatment 1 (N=xx) n (%)
Number of TEAEs		Mild	x (xx.x)
		Moderate	x (xx.x)
		↓	
Gastrointestinal disorders	Total number of patients	Mild	x (xx.x)
		Moderate	x (xx.x)
	Abdominal discomfort	Mild	x (xx.x)
	Abdominal pain	Mild	x (xx.x)
		↓	

Source: Listing 16.2.xx

n = number of patients (patients with >1 TEAE are counted only once per system organ class and preferred term)

*Coded using MedDRA version xx.x

*Programming notes: Each preferred term counted only once across all severities for each patient
SOCs and PTs are sorted in decreasing order of frequency
Presented for all applicable MedDRA system organ classes and terms.*

Template T_AE4

Table 14.3.3.xx Summary of treatment-emergent adverse events by day of onset

System Organ Class*	Preferred Term	Day of Onset	Treatment 1 (N=xx n (%))
Nervous system disorders	Dizziness	Day 0	x (xx)
		Days 1-6	x (xx)
		>=Day 7	x (xx)
	Headache ↓	Day 0	x (xx)
		Days 1-6	x (xx)
		>=Day 7	x (xx)
Gastrointestinal disorders	Abdominal discomfort	Day 0	x (xx)
		Days 1-6	x (xx)
		>=Day 7	x (xx)

Source: Listing 16.2.xx

n = number of patients

*Coded using MedDRA version xx.x

*Programming notes: SOCs and PTs are sorted in decreasing order of frequency
Presented for all applicable MedDRA system organ classes and terms.*

Template T_LB4

Table 14.3.4.xx Summary of post dose clinically significant abnormal laboratory values by treatment and planned relative time

Laboratory Test (units)	Treatment	Planned Relative Time	Clinically Significant n (%)
Treatment 1 (N=xx)			

Source: Listing 16.2.xx

Programming notes: Continued with all tests, and time points.

Template T_LB2

Table 14.3.5.xx Summary of chemistry laboratory values

Laboratory Test (units)	Treatment	Planned Relative Time	n	Mean	SD	Median	Min	Max	Change from Baseline					
									n	Mean	SD	Median	Min	Max
									Treatment 1 (N=xx)					

Source: Listing 16.2.xx

Programming notes: Continued with all time points

Template T_VS1

Table 14.3.6.xx Summary of vital signs

									Change from Baseline					
Variable (units)	Treatment	Planned		Mean	SD	Median	Min	Max						
		Relative Time	n						n	Mean	SD	Median	Min	Max
Systolic Blood Pressure (mmHg)	Treatment 1 (N=xx)													

Source: Listing 16.2.xx

Programming notes: Continued with all variables, and time points

Template T_VS2

Table 14.3.6.xx Summary of vital signs of potential clinical importance

Treatment	Planned Relative Time	Systolic Blood Pressure (mmHg)		Diastolic Blood Pressure (mmHg)		Heart Rate (beats/min)		Temperature (C)		etc	
		n	(%)	n	(%)	n	(%)	n	(%)	n	(%)
Treatment 1 (N=xx)	Time 1										
	Time 2										

Source: Listing 16.2.xx

Programming notes: Continued with all parameters. n = total number of results for that parameter

Template T_VS3

Table 14.3.6.xx Summary of vital signs of potential clinical importance by parameter and treatment (excluding baseline time point)

Treatment	Systolic Blood Pressure (mmHg)		Diastolic Blood Pressure (mmHg)		Heart Rate (beats/min)		Temperature (C)		etc		Overall*	
	n	(%)	n	(%)	n	(%)	n	(%)	n	(%)	n	(%)
Treatment 1 (N=xx)												

Source: Listing 16.2.xx

Patients only counted once per parameter

*Patients only counted once per treatment

Programming notes: Continued with all parameters. n = total number of results for that parameter
Only include post-treatment time points

Template T_VS4

Table 14.3.6.xx Summary of post dose clinically significant vital signs

Treatment	Planned Relative Time	Clinically Significant	
		n	(%)
Treatment 1 (N=xx)	Time 1 Time 2		

Programming notes: Continued with all timepoints. n = total number of results for that parameter

Template T_VS5

Table 14.3.7.xx Summary of peak Vital Signs ranges by treatment, ranges and parameter - Day 0 post dose

	Systolic Blood Pressure (mm Hg)										
	<130	130 - 139	140 – 149	150 – 159	160 – 169 n	170 – 179	180 – 189	190 – 199	200 - 209	210 – 219	> =220
Treatment	n (%)	n (%)	n (%)	n (%)	(%)	n (%)	n (%)	n (%)	n (%)	n (%)	n (%)
Treatment 1 (N=xx)											

Source: Listing 16.2.xx

The maximum value across all time points per subject is used for analysis.

Programming notes: Continued with all variables . n = total number of results for that parameter.
Continued with all the ranges in **section 14.8.1**

Template T_VS6

Table 14.3.6.xx Summary of peak vital signs by treatment and parameter - baseline and Day 0 post dose

Variable (units)	Treatment	Planned Relative Time	n	Mean	SD	Median	Min	Max
Systolic Blood Pressure (mmHg)	Treatment 1 (N=xx)	Predose Day 0, Postdose						

Source: Listing 16.2.xx

Programming notes: Continued with DBP and HR. The maximum value across all time points per subject are used for analysis.

Template T_EG2

Table 14.3.7.xx Summary of ECG values

Variable (units)	Treatment	Planned Relative							Change from Baseline					
		Time	n	Mean	SD	Median	Min	Max	n	Mean	SD	Median	Min	Max
Heart Rate (bpm)	Treatment 1 (N=xx)													
PR Interval (msec)	Treatment 1 (N=xx)													

Source: Listing 16.2.xx

Programming notes: Continued with all time points
Do not summarise RR or QRS axis

Template T_EG3

Table 14.3.7.xx Summary of QTcF values and changes in QTcF values of potential clinical importance

Treatment	Planned Relative Time	451 – 480 msec		481 – 500 msec		> 500 msec		>30-60 msec Increase		>60 msec Increase	
		n	(%)	n	(%)	n	(%)	n	(%)	n	(%)
Treatment 1 (N=xx)	Time 1										
	Time 2										
	Time 3										

Source: Listing 16.2.xx

Programming notes: Continued with all time points. n = total number of results for that parameter

Template T_EG5

Table 14.3.7.xx Summary of clinically significant ECG values

Treatment	Planned Relative Time	Abnormal CS	
		n	(%)
Treatment 1 (N=xx)	Time 1		
	Time 2		

Source: Listing 16.2.xx

Programming notes: Continued with all timepoints. n = total number of results for that parameter
For cardiac telemetry, change planned relative time to Start and End date/time

Template T_RDQ

Table 14.3.7.xx Summary of readiness of discharge questionnaire (RDQ)- Time to discharge (units)

Treatment	Planned Relative Time	n	Mean	Median	Min	Max
Treatment 1 (N=xx)						

Source: Listing 16.2.xx

Programming notes: Continued with all time points

Template T_ReAQ_PG _

Table 14.3.8.xx Summary of re-activation questionnaire (ReAQ)

Assessment	Planned Relative Time	Treatment 1 (N=xx)
Number of Patients with Re-activation (%)	Time 1	Yes
		No
Number of Days after dose (Days)	Time 1	n
		Mean
		SD
		Median
		Min
		Max
Number of Re-activation events	Time 1	n
		Mean
		SD
		Median
		Min
		Max
Emotional Valence	Time 1	Mostly Positive
		Neutral
		Mostly Negative
Functional Impact- Work (%)	Time 1	None
		Mild
		Moderate
		Severe
Functional Impact- Social Life (%)	Time 2	
	Time 1	None
		Mild
		Moderate
		Severe
	Time 2	

Functional Impact- Family Life (%)	Time 1	None Mild Moderate Severe
<hr/>		

[figure not shown]
Source: Listing 16.2.xx

Programming notes: *Continued with all assessments and timepoints. Occurrence =Number of patients with Re-activation).*
Denominator for percentages will be total number of scores recorded (excluding N/A) at relative time point

